# USUAL CARE GROUP (Fentanyl PLUS Saline)

- 1. Saline Loading Dose (Placebo, Infusion) =
  - An identical volume of saline as that in 0.3 mg/kg of ketamine. This will be initiated approximately 10 minutes prior to start of wound care with pump set to deliver saline slowly over approximately 5 minutes (i.e., during the same time and at the same rate that the Ketamine group receives the ketamine loading dose).

- 2. Fentanyl (UC, injection) =
  - 1 mcg / kg: This is given to participants in both Group 1 and Group 2 initiated < 1 minute prior to wound care.
- 3. Saline (Placebo, Infusion) =
  - Identical volume of fluid as that in 2.5 mcg/kg/min of ketamine, with the pump set to initiate infusion immediately following the Loading Dose and continued for the duration of the session. The EPIC order set specifies that the nurse determines when the session is over, and that the nurse will turn off the infusion at that point.

# PRN DOSE\*

PRN Fentanyl PRN (UC, injection) = 1 mcg / kg.

\*The PRN is provided to participants in both Group 1 and Group 2 when a participant requires additional pain medication. The criteria for providing PRN fentanyl are based on customary nursing practices, including a self-reported persistent rise in NAS pain > 2/10 or a NAS ≥ 7/10 (JCAHO standard) and combined with nursing judgment.

# 1. Protocol Changes and Clarifications Include:

a) \*Loading Dose Start Time (see Text, below): Previously, the ketamine loading dose had been slated to start 20 minutes prior to the start of wound care, and the placebo "loading dose" was slated to start 10-minutes prior to the start of wound care. Burn, Critical Care and Pharmacy collaborators have subsequently agreed that it is preferable to start the loading doses at the same time for both groups. Thus, loading doses of randomly assigned, ketamine or placebo (saline) will be administered to participants in the Usual Care condition (placebo) and the Usual Care Plus Ketamine Augmentation condition (ketamine), starting at approximately 10-minutes prior to initiation of dressing change/wound care.

- 2. The protocol now specifies that
  - i. the loading dose of ketamine OR saline will be delivered by pump set at approximately 5 minutes by the nurse to deliver the medication at standardized slow rate.
  - ii. \* Behavioral Equivalence: Administration of loading doses simultaneously, regardless of group assignment, will maintain the naïve / blinding of provider / nurse / participant.
  - iii. \* Pharmacokinetic Properties: The pharmacokinetics of ketamine (absorption, metabolism, half-life, excretion) are sufficient to allow for ketamine to be administered approximately 10 minutes prior to fentanyl, versus the previously planned 20-minute lag in start times.

## b. PRN Fentanyl Medications: Pain Assessment Before, During and After Wound Care Session.

Criteria for PRN: The study protocol will use the JHBC standard-of-care method for rating pain and the need for additional analgesic medications before, during and following wound care. That is, as part of standard-of-care, pain is routinely assessed before, during and after wound care by the Registered Nurse/Wound Care Tech (RN / Tech) to determine whether there is a need for additional pain medications. This standard-of-care pain rating process will be applied in this study protocol. The RN / Tech will ask participants to rate their pain before the ketamine / placebo loading dose administration approximately 10 minutes prior to the start of each wound care session, during the wound care session when clinical observations suggest pain assessment is indicated, and, after wound care session ends. At each of these times, when the RN / Tech asks participants to rate their present pain intensity (PPI) on Numeric Analogue Scale (NAS: 0-10), those participants who rate their PPI/NAS as  $\geq$ 7/10, or, whose pain severity has risen  $\geq$ 2/10, will be asked the following:

- i. The RN / Tech asks the participant "Do you need additional pain medication?"
- ii. If the participant says "Yes" then the PRN medication is administered (1 mcg/kg-based fentanyl, injected).
- iii. If participant says "No" then the PRN medication is not administered.
- iv. The RA will record, on a standard form, the PPI/NAS that the RN was given, whether a PRN was offered (Y/N), whether the participant accepted (Y/N), what drug / dose /

delivery method were utilized, and elapsed time since loading dose or, the previous PRN analgesic administration.

# PRN DOSE (Fentanyl)\*

# PRN Fentanyl PRN (UC, injection) = 1 mcg / kg.

\*The PRN is provided to participants in both Group 1 and Group 2 when a participant requires additional pain medication. The criteria for providing PRN fentanyl are described next:

\*PRN – Standard of Care: Pain Severity for PRN Administration: The PRN is provided to participants in either Group 1 or Group 2 when a participant requires additional pain medication. In this protocol, the nurse will consider providing PRN fentanyl, if the participant's self-reported absolute pain severity is  $\geq$ 7/10 (JCAHO), **OR**, there is a persistent rise in pain severity that is  $\geq$ 2/10 above the most recent NAS rating. This protocol for providing PRN fentanyl takes into consideration both the standard nursing practice (i.e., persistent rise in pain severity  $\geq$ 2/10) as well as the JCAHO-standard cutoff for treating pain severity (i.e.,  $\geq$ 7/10).

\*PRN – Limit before Alternative Approaches are Considered: After each PRN fentanyl injection, no further PRN fentanyl should be given for at least 15minutes to allow time for the medication to have its effect and to prevent over-medication. It is recommended that consideration of alternative approaches be undertaken after 3 PRN fentanyl injections (i.e., three injections of "1 mcg / kg of PRN fentanyl") as described below. It is also recommended that if there is a failure to reduce pain intensity by  $\geq$  2/10 after at least 15minutes after PRN administration, another PRN or alternative medication be considered.

The maximum number of PRN fentanyl administrations as well as any alternative approaches will be decided at the discretion of the wound care nurse and the provider on the basis of their Best Care Practices and the consideration of each specific participant's circumstances.

\*PRN – Nursing / Provider Judgment: Furthermore, when determining the patient's need for additional analgesic or alternative medication, the trained and experienced BICU nurse and provider often employ assessment of factors other than self-reported pain intensity. These additional factors will also be utilized by the wound care nurse and provider in deciding what medication is or is not necessary during this "Ketamine for Acute Pain During Burn Wound Care" protocol.

#### Summary of Medication Dose, Timing, Method:

- a. The Fentanyl loading dose will begin <1 minute prior to each wound care session for both the Usual Care and the Ketamine Augmentation groups.
- b. The drug delivery mechanism for the loading dose of ketamine / placebo, as well as all of the continuous infusions, will be via identical masked / nondescript infusion bags. The ketamine / placebo contents will be delivered at identical volumes and continued for the duration of the wound care session in order to preserve the blind.
- c. The blinded infusion bags will be used to deliver both ketamine and saline and will be prepared and provided by the JHBMC pharmacy ([name]). The pump will be programmed by the JHBC nurse based on the provider's prescription, the randomization schedule and the EPIC order set (displayed in EPIC and on infusion bag label).
- d. Wound Care Protocol and Outcome Protocol Duration:

i. Study / Follow-up Protocol: Eligibility determination (ED); consent procedures; informed consent signed (as soon as possible post-admission to the BICU); randomization; initial wound care protocol soon after consented, (1st wound care optimal); twice daily (preferred) wound care (potential range 0-2 sessions daily: there may be days on which no wound care is performed for various reasons such as dressing type, post op, etc) protocol for 7 consecutive days (potential range 3-7 days); Follow-up 1 day, 1-week and 1-month after last of the 7-day study protocol for a total of 5 weeks or n= 35 days per participant.

ii. Wound Care Study Protocol: Includes pretest assessment, premedication (loading dose), wound care and interim infusion and assessments, posttest assessments. Each wound care procedure including assessments will take approximately 1-2 hours.

ii. Ketamine for Acute Burn Pain During Burn Wound Care Protocol: Twice daily wound care sessions, estimated length of hospitalization on BICU is ≥5 days (range = 3 - 7 days).

2. Burn Center 5-year Average population meeting Key Inclusion Criteria

[name], MSN, Trauma Coordinator, provided the speadsheets with the admissions data. [name] is Trauma Coordinator for the trauma and burns at JHBMC and maintains datasets for the Maryland Institute for Emergency Medical Services Systems (MIEMSS) and the American Burn Association (ABA) Registry and has access to all data from the JHBC entered in these systems.

[name] used these data to estimate available sample size of eligible admissions (see Table below). The admissions data enable him to render a more accurate and reliable estimate of eligible admissions for the present study. The most accurate predictor for the number of patients that we anticipate will be admitted to the JHBC during the next 12 months comes from the database of JHBC admissions in the past. We selected the past 5 years of admissions data in order to stabilize means and standard deviations of monthly and annual admissions meeting inclusion and exclusion criteria. From these hard numbers, [name] employed the means described next to estimate the number of eligible patients who are admitted to the Johns Hopkins Burn Center that will be approached, offered informed written consent, and to initiate the protocol and to complete the 7-day protocol and the 1-week and 1-month outcome assessments.

Patient Admissions 2012 – 2016: BOTH TBSA Between 2% & 40% AND Age ≥18 years old & ≤70 years old						
	2012	2013	2014	2015	2016*	Annual Average
Admits (n ) w/ average LOS ≥5.5 Days	140	135	143	116	53	128
Average age w/ LOS ≥5.5 Days, mean (SD)	42.5 (13.25)	43.3 (13.65)	42.8 (13.52)	42.4 (13.17)	38.6 (14.56)	42.4 (13.53)
Average TBSA (2 nd + 3 rd ) w/ LOS ≥5.5 Days, mean (SD)	8.2 (7.05)	8.6 (7.78)	7.8 (6.95)	9.2 (7.38)	7.1 (6.50)	8.3 (7.21)
Admits w/ LOS ≥7 Days, n (%)	91 (25.9%)	80 (22.8%)	81 (23.1%)	74 (21.1%)	23 (6.6%)	74
Average age w/ LOS ≥7 Days, mean (SD)	42.0 (13.29)	45.7 (12.48)	43.9 (13.40)	43.6 (13.27)	40.5 (15.39)	43.6 (13.30)
Average TBSA (2 nd + 3 rd ) w/ LOS ≥7 Days, mean (SD)	8.9 (7.93)	10.0 (9.13)	9.3 (8.14)	10.5 (8.46)	9.0 (8.30)	9.6 (8.36)

Table 1. Inclusion Criteria for past 5 years

\*2016 Based on only 6 months of data

The Ketamine team makes eligibility determination, initiates consent procedures, and the Informed Consent is signed (as soon as possible post-admission). The team then proceeds with initial wound care protocol after consented, (1st wound care optimal) and continues twice daily wound care for 7 days and 14 wound care sessions. The scheduled outcome assessments are on 1-day, 1-week and 1-month after the

last study wound care session for a total of 5 weeks or n= 35 days. The actual minimum length of stay may be  $\geq 3$  - 5.5 consecutive days and  $\geq 6-11$  wound care sessions (see Sample Size Calculations – next).

3. Sample Size and Power Estimations – Additional Biostatistics, Epidemiology And Database Resources [name], Psychologist, Statistician

[name], Epidemiologist/Biostatistician, Statistician

Drs. [name] and [name] participated in planning, executing, interpreting and writing/illustrating the rich analyses of primary (i.e., pain severity, opiate sparing), and secondary (i.e., symptoms of PTSD and depression) aims. The Biostatistics, Epidemiology and Data Management Core (BEAD) is a recognized research Core of the JHU School of Medicine which provides research support services to faculty and trainees. With sponsored funds from the Vice Dean for Research of the Bayview Medical Campus, BEAD Core research support will be available to support this research project. At a minimum, this can include 60 hours of support services to include research support, trainee career development and subsequent grants development activities based on the results of this investigation.

Furthermore, the sponsored research resources of ICTR will stretch the budget and allow the Ketamine Project to optimize the rigor in database design and management, as well as with overall biostatistical guidance leveraging the Core's team of Masters and PhD level biostatisticians and epidemiologists with wide ranging content and methodologic expertise. Engagement of these services will ensure the quality of the data being compiled, integrated and utilized as this is a vital component of the success of the intervention project and the overall objectives of the study through the engagement in the development of the database structure, variable coding, data input, data manipulation and transformations required for the seamless transition for the conduct of analyses.

The sample size estimates described next were generated by [name], BEAD statistician, as Co-Investigator on the project for the role and tasks delineated here. The next two paragraphs describe the methods and conclusions used by [name] to Estimate sample sizes for:

- 1. Sample Size Estimate: 7-day LOS, as originally planned, and
- 2. Sample Size Estimate/Corrected: 7-Day LOS as corrected to 5.5 Days (11 wound care sessions see rationale below) due to uncertainties not always evident or predictable on the first day of admission but which may affect/reduce LOS for any given patient.

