# c. Blinding

The Safety, Efficacy and Opiate-Sparing Effects of Ketamine for Acute Burn Wound Care Pain in a Setting Analogous to Austere Battlefield Conditions (IRB00089761) provides for 3-levels of blind: nurse at bedside, patient-participant, and research assistant with the following methods:

The investigational pharmacy will provide blinded medications (i.e., usual care with normal saline or usual care with ketamine augmentation) for this study (for details, see above). The provider will order the medications, the pharmacy will fill the order in identical delivery systems and deliver it to Pyxis in the BICU, thus resulting in blinding to the content of the injections and infusions for the nurse who administers these medications, the research assistant and the patient. This is necessary to ensure fidelity of procedures and validity of findings, responses, observations and data collection. This procedure reduces the possibility that preconceived notions could influence clinical or research personnel or participant in the study.

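### The plan lists the randomization schedule among the inputs a blinded nurse uses to program the pump, and elsewhere gives pump programming to pharmacy

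*Combined protocol and SAP*

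**What the plan says.** Section 4, Summary of Medication Dose, Timing, Method, item c, says of the pump: "The pump will be programmed by the JHBC nurse based on" three inputs. One is what the provider has prescribed; the other two are given as "the randomization schedule and the EPIC order set (displayed in EPIC and on infusion bag label"). Item b of the same summary says that the ketamine or placebo "contents will be delivered at identical volumes and continued for the duration of the wound care session in order to preserve the blind". The saline arm's continuous infusion is specified as "Identical volume of fluid as that in 2.5 mcg/kg/min of ketamine".

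Protocol Changes and Clarifications, item 2.i, says that the loading dose in either arm "will be delivered by pump set at approximately 5 minutes by the nurse to deliver the medication" at a slow, standardized rate. Item 2.ii gives the purpose of simultaneous loading doses as maintaining the "blinding of provider / nurse / participant".

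Section 4c, Blinding, lists three blinded levels: "nurse at bedside, patient-participant, and research assistant". It describes pharmacy supply in identical delivery systems as "resulting in blinding to the content of the injections and infusions for the nurse who administers these medications". The design statement after the exclusion criteria also counts the nurse among the three blinded parties.

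Section 8 reads differently on the pump. The account of pharmacy's role (item iv) has the pharmacist randomize each participant from the schema and send identical bags with blinded labels. The nursing policy has RNs put up and start an infusion whose rates are already in the pump. It says that pharmacy presets the loading dose and rate, that the study pharmacist preprograms the pump, and that nursing staff do not know the arm.

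**The concern.** Two conflicts appear. The first is over who programs the pump: nursing in section 4, pharmacy in section 8. The second is more serious for the trial's inference. Item c names the randomization schedule as something the nurse works from, although nurses are meant to be blinded and no section creates an unblinded nurse role.

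At stake is the second primary aim, opiate sparing, which is measured by the number of requests for additional analgesic in each wound care session. Nursing staff are part of the process that produces that count. If they knew the arm, the timing of pain questions and the use of judgment about PRN fentanyl could differ between arms for reasons other than the drug.

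**Working it through.** No figure in the plan bears on this point, so the check sets the sections side by side.

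1. **Who programs the pump.** Summary of Medication Dose, item c: the JHBC nurse. Protocol Changes, item 2.i, which is written as what the protocol now specifies: the nurse sets the loading-dose delivery time. Section 8 nursing policy: pharmacy presets, and the study pharmacist preprograms. These cannot all be followed. Item 2.i bears only on who sets the pump; the delivery time is the same in both arms and reveals nothing about allocation.

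2. **Who holds the schedule.** Section 8, pharmacy's role, item iv: the pharmacist randomizes from the schema. Summary of Medication Dose, item c: the schedule is one of three inputs to the nurse's programming, listed separately from the prescription and the order set.

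3. **Whether the schedule can reveal the arm.** The Randomization paragraph in section 4 assigns odd numbers to saline and even numbers to ketamine. Anyone who has the list and knows that rule can read the allocation.

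4. **Whether the nurse is blinded.** The design statement, Protocol Changes item 2.ii, section 4c and the section 8 nursing policy all say so. Section 4c refers to the nurse at the bedside and to the nurse who administers the medication, and it is an inference that the JHBC nurse of item c is that person. The conflict does not depend on the inference, because the nursing policy covers nursing staff generally.

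5. **Whether the nurse needs the schedule.** Volumes are identical in both arms for the loading dose and the continuous infusion. The text gives no reason why setting the pump would require knowing the arm.

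6. **How knowledge of the arm could reach the outcome.** Under Criteria for PRN, the RN or technician asks for a pain rating before the loading dose, after the session, and during the session when clinical observation suggests it. A rating of at least 7/10, or a rise of at least 2/10, leads to a fixed question on whether more medication is needed. The participant answers yes or no, and the research assistant records the rating, the offer and the acceptance. The paragraph on nursing and provider judgment allows factors beyond the rating to enter the decision. The discretion therefore lies in when the in-session rating is requested and in that judgment. The study's own ratings every 10 minutes (Specific Aim #1) follow a fixed schedule, but the PRN criteria do not tie the question to them. This step assumes that a yes to the PRN question counts as a request, which Specific Aim #2 does not spell out.

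7. **Size.** The documents give no request rate, no variance for the count and no measure of nurse influence. Neither the size nor the direction of a bias can be calculated.

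**The case against.** The strongest reply is that item c is loosely worded and no more. It sits in a paragraph about blinded bags, and its sentence ends by pointing to what is displayed in EPIC and on the bag label. The label is blinded, the prescriber is said to be blinded in several places, and the pharmacist does the randomizing. One phrase stands against repeated statements that the nurse is blinded. The Manual of Operations and the drug and order builds, which are not part of these documents, may settle who sets the pump.

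Much of this stands. Loose drafting is plausible, and the documents do not show that any nurse receives the list in practice. The milder reading is not what the sentence says, however. The schedule is named as an input in its own right, and no section expressly says that the EPIC order hides the arm. An operations manual could settle practice, but the protocol would still contradict itself.

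It is also fair that the nurse does not produce the pain score. The participant gives the rating and answers the PRN question, and the research assistant documents both. This narrows the route to the Aim 2 count without closing it.

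A reader might infer that the blind was broken or that the Aim 2 comparison is biased. The documents support neither: they show a possible route under a literal reading, not an event. Nor do they settle whether Aim 1 is exposed. They do not say who applies the fingertip pressure for the hyperalgesia ratings, so an effect there can be neither asserted nor ruled out.

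**Conclusion.** The contradiction is real and is in current text. Pump programming is given to both nursing and pharmacy, and the randomization schedule is named as an input for staff described as blinded. Followed literally, item c opens a route to allocation for people who influence when the PRN question arises and whose judgment enters PRN decisions. That bears on a primary outcome in a trial whose design rests on blinding.

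The consequence is conditional. It requires that item c be followed as written, that the schedule in the nurse's hands be readable by arm, and that knowledge of the arm alter the timing of ratings or PRN judgment. The size of any bias cannot be estimated. The wording should be fixed because the phrase serves no function in setting the pump and contradicts the stated blind.

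**What to change.** - Strike the randomization schedule from the nurse's inputs in Summary of Medication Dose, Timing, Method, item c.
- State that nursing staff have no access to the schedule, and that the EPIC order and bag label visible to them do not show the arm. The second part is needed because, if the order displayed the arm, removing the phrase alone would leave the route open. The restriction applies to nursing staff, not to the pharmacist, who knows the allocation by role.
- Reconcile Protocol Changes item 2.i, Summary of Medication Dose item c, section 4c, and the pharmacy and nursing-policy text in section 8, so that one role is named as programming the pump.

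No sample size or analysis changes. Identical volumes mean that the nurse loses nothing needed to set the pump, and pharmacy already randomizes and supplies bags with blinded labels. The cost is wording, plus a check that the EPIC display does conceal the arm. If it does not, the order display would need changing as well.

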#### 1. Sample Size Estimate Based on Stay $\geq$ 7 days in Burn ICU.

The sample size calculation is based on the primary statistical procedure for this project which will test the difference in mean pain scores, defined as the average self-report of mean pain score, based on the Numeric Analogue Scale (NAS), during each burn wound care procedures, between individuals randomized to usual care plus placebo (fentanyl plus saline) and those randomized to the intervention arm (usual care + ketamine). PASS Sample Size (Version 14) was used to perform all sample size calculations while considering individuals over the one-year study duration randomized to control and intervention arms in a 1:1 fashion.

In the first case, we further assume that each individual, will, on average, have a length of stay of 7 days thus resulting in 14 wound care procedures performed during hospital stay. We determined the minimum sample size for our trial based on 80% power at p = 0.05 to detect a clinically significant difference in mean pain score during the wound care procedure of 2.0 points between the control and intervention arms with a standard deviation of 3.0. In addition, to account for the clustered nature of procedures performed on individuals, we have used a sample size inflator (also termed "design effect") of 10.1 as described by the Cochrane manual@ conservatively using an interclass correlation of effects of 0.7 amongst repeated measures of pain scores within each individual and 14 observations per individual.

The required sample size needed to accept the alternative hypotheses that the mean pain care score in the intervention arm decreased by 2 points compared to the control arm at the 0.05 level would require 27 individuals per arm (54 total), our anticipated population of 74 eligible individuals is adequate to show a clinically significant improvement for both intervention arms.

@http://handbook.cochrane.org/chapter\_16/16\_3\_4\_approximate\_analyses\_of\_cluster\_randomized\_trials\_for\_a.htm

